14.1.3 Missing AE start day only [namely, dd in dd-mm-yyyy is missing]

- If $yyyy(AE) = yyyy(1^{st} \text{ day of study medication})$, then
 - If $mm(AE) = mm(1^{st} \text{ day of study medication})$, then
 - $dd(AE) = dd(1^{st} \text{ day of study medication})$
 - If $mm(AE) > mm(1^{st} \text{ day of study medication})$, then
 - $dd(AE) = 1$
 - If $mm(AE) < mm(1^{st} \text{ day of study medication})$, then

- $dd(AE) = \text{last day of mm}(AE)$
- If $yyyy(AE) < yyyy(1^{\text{st}} \text{ day of study medication})$, then
 - If AE stop date exists and is complete, then
 - $dd(AE) = dd(AE \text{ stop});$
 - if AE stop date does not exist or is incomplete, then
 - $dd(AE) = \text{last day of mm}(AE)$
- If $yyyy(AE) > yyyy(1^{\text{st}} \text{ day of study medication})$, then
 - $dd(AE) = \text{first day of mm}(AE)$

14.2.1 Missing AE stop day and month [namely, dd & mm in dd-mm-yyyy are missing]

- If $yyyy(AE) = yyyy(\text{last day of study medication})$, then
 - $dd(AE) = dd(\text{last day of study medication})$
 - $mm(AE) = mm(\text{last day of study medication})$
- If $yyyy(AE) < yyyy(\text{last day of study medication})$, then
 - $dd(AE) = 31$
 - $mm(AE) = \text{December}$
- If $yyyy(AE) > yyyy(\text{last day of study medication})$, then
 - $dd(AE) = 1$
 - $mm(AE) = \text{January}$

14.2.2 Missing AE stop month only [namely, mm in dd-mm-yyyy is missing]

- If $yyyy(AE) = yyyy(\text{last day of study medication})$, then
 - $mm(AE) = mm(\text{last day of study medication})$
- If $yyyy(AE) < yyyy(\text{last day of study medication})$, then
 - $mm(AE) = \text{December}$
- If $yyyy(AE) > yyyy(\text{last day of study medication})$, then
 - $mm(AE) = \text{January}$

14.2.3 Missing AE stop day only [namely, dd in dd-mm-yyyy is missing]

- If $yyyy(AE) = yyyy(\text{last day of study medication})$, then
 - If $mm(AE) = mm(\text{last day of study medication})$, then

- $dd(AE) = dd(\text{last day of study medication})$
- If $mm(AE) > mm(\text{last day of study medication})$, then
 - If AE start date exists and is complete, then
 - $dd(AE) = dd(\text{AE start});$
 - if AE start date does not exist or is incomplete, then
 - $dd(AE) = \text{first day of } mm(AE)$
- If $mm(AE) < mm(\text{last day of study medication})$, then
 - $dd(AE) = \text{last day of } mm(AE)$
- If $yyyy(AE) < yyyy(\text{last day of study medication})$, then
 - $dd(AE) = \text{last day of } mm(AE)$
- If $yyyy(AE) > yyyy(\text{last day of study medication})$, then
 - If AE start date exists and is complete, then
 - $dd(AE) = dd(\text{AE start});$
 - if AE stop date does not exist or is incomplete, then
 - $dd(AE) = \text{first day of } mm(AE)$

15.2 Appendix B: Myelodysplastic Syndromes World Health Organization Classification System

| Myelodysplastic Syndromes WHO Classification System | | |
|--|---|--|
| Category | Definition | |
| | Peripheral Blood Smear Evaluation | Bone Marrow Evaluation |
| Refractory cytopenia with unilineage dysplasia (RCUD): (refractory anemia [RA]; refractory neutropenia [RN]; refractory thrombocytopenia [RT]) | Unicytopenia or bicytopenia ^a No or rare blasts (< 1%) ^b | Unilineage dysplasia: ≥ 10% of the cells in one myeloid lineage < 5% blasts < 15% of erythroid precursors are ringed sideroblasts |
| Refractory Anemia With Ringed Sideroblasts (RARS) | Anemia No blasts | ≥ 15% of erythroid precursors are ringed sideroblasts Erythroid dysplasia only < 5% blasts |
| Refractory Cytopenia With Multilineage Dysplasia (RCMD) | Cytopenia(s) No or rare blasts (< 1%) ^b No Auer rods < 1x10 ⁹ /L monocytes | Dysplasia in ≥ 10% of the cells in ≥ 2 myeloid lineages (neutrophil and/or erythroid precursors and/or megakaryocytes) < 5% blasts in marrow No Auer rods ± 15% ringed sideroblasts |
| Refractory Anemia With Excess Blasts-1 (RAEB-1) | Cytopenias < 5% blasts ^b No Auer rods < 1x10 ⁹ /L monocytes | Unilineage or multilineage dysplasia 5%-9% blasts ^b No Auer rods |
| Refractory Anemia With Excess Blasts-2 (RAEB-2) | Cytopenias 5%-19% blasts ^c Auer rods ^c < 1x10 ⁹ /L monocytes | Unilineage or multilineage dysplasia 10%-19% blasts ^c Auer rods ± ^c |
| Myelodysplastic Syndrome - Unclassified (MDS-U) | Cytopenias < 1% blasts ^b | Unequivocal dysplasia in < 10% of cells in one or more myeloid lineages when accompanied by a cytogenetic abnormality considered as presumptive evidence for a diagnosis of MDS ^d |
| MDS Associated With Isolated del(5q) | Anemia Usually normal or increased platelet count No or rare blasts (< 1%) | Normal to increased megakaryocytes with hypolobated nuclei |

| | | |
|--|--|--|
| | | < 5% blasts Isolated del(5q) cytogenetic abnormality No Auer rods |
|--|--|--|

^a Bicytopenia may occasionally be observed. Cases with pancytopenia should be classified as MDS-U.

^b If the marrow myeloblast percentage is < 5% but there are 2% to 4% myeloblasts in the blood, the diagnostic classification is RAEB-1. Cases of RCUD and RCMD with 1% myeloblasts in the blood should be classified as MDS-U.

^c Cases with Auer rods and < 5% myeloblasts in the blood and less than 10% in the marrow should be classified as RAEB-2. Although the finding of 5% to 19% blasts in the blood is, in itself, diagnostic of RAEB-2, cases of RAEB-2 may have 5% blasts in the blood if they have Auer rods or 10% to 19% blasts in the marrow or both. Similarly, cases of RAEB-2 may have < 10% blasts in the marrow but may be diagnosed by the other 2 findings,

Auer rods + and/or 5% to 19% blasts in the blood.

^d Includes unbalanced abnormalities -7 or del(7q), -5 or del(5q), i(17q) or t(17p), -13 or del(13q), del(11q), del(12p) or t(12p), del(9q), idic(X)(q13), balanced abnormalities t(11;16)(q23;p13.3), t(3;21)(q26.2;q22.1), t(1;3)(p36.3;q21.1), T2;11(p21;q23), inv(3)(q21q26.2), and t(6;9)(p23;q34), and complex karyotype (3 or more chromosomal abnormalities) involving one of more of the listed abnormalities.

Sources:

15.3 Appendix C: International Prognostic Scoring System Score

| International Prognostic Scoring System for MDS | | | | | |
|---|-------------|--------------|------|-------|-------|
| Prognostic Variable | Score Value | | | | |
| | 0 | 0.5 | 1.0 | 1.5 | 2.0 |
| Bone Marrow Blasts (%) | < 5 | 5-10 | - | 11-20 | 21-30 |
| Karyotype ^a | Good | Intermediate | Poor | | |
| Cytopenias ^b | 0 or 1 | 2 or 3 | | | |

^a Good: normal, -Y, del(5q), del(20q); Poor: complex (≥ 3 abnormalities) or chromosome 7 anomalies;
 Intermediate: other abnormalities.

^b Defined as: Hemoglobin < 100 g/L, absolute neutrophil count < $1.5 \times 10^9/L$, and platelet count < $100 \times 10^9/L$.

Note: Scores for risk groups are as follows: Low = 0; INT-1 = 0.5-1.0; INT-2 = 1.5-2.0; and High: ≥ 2.5

Source:

15.4 Appendix D: ECOG Performance Status

| ECOG Performance Status | |
|-------------------------|--|
| Grade | ECOG |
| 0 | Fully active, able to carry on all pre-disease performance without restriction. |
| 1 | Restricted in physically strenuous activity but ambulatory and able to carry out work of a light or sedentary nature, e.g., light house work, office work. |
| 2 | Ambulatory and capable of all self-care but unable to carry out any work activities. Up and about more than 50% of waking hours. |
| 3 | Capable of only limited self-care, confined to bed or chair more than 50% of waking hours. |
| 4 | Completely disabled. Cannot carry on any self-care. Totally confined to bed or chair. |
| 5 | Dead. |

Source: Oken MM, Creech RH, Tormey DC, Horton J, Davis TE, McFadden ET, et al. Toxicity and response criteria of the Eastern Cooperative Oncology Group. *Am. J. Clin. Oncol.* 1982;5(6):649-55.

15.5 Appendix E: Hematologic Response According to the IWG Criteria for MDS

| Modified Hematologic Response According to IWG Criteria for MDS | |
|--|--|
| Category | Response criteria (responses must last at least 4 weeks) |
| Complete Remission (CR) | Bone marrow: $\leq 5\%$ myeloblasts with normal maturation of all cell lines ^a Persistent dysplasia will be noted ^{a,b} Peripheral blood ^c Hgb ≥ 11 g/dL Platelets $\geq 100 \times 10^9/L$ Neutrophils $\geq 1.0 \times 10^9/L^b$ Blasts 0% |
| Partial Remission (PR) | All CR criteria if abnormal before treatment except: Bone marrow blasts decreased by $\geq 50\%$ over pretreatment but still $> 5\%$ Cellularity and morphology not relevant |
| Marrow CR ^b | Bone marrow: $\leq 5\%$ myeloblasts and decrease by $\geq 50\%$ over pretreatment ^b Peripheral blood: if HI responses, they will be noted in addition to marrow CR ^b |
| Stable Disease (SD) | Failure to achieve at least PR, but no evidence of progression for > 8 wks |
| Failure | Death during treatment or disease progression characterized by worsening of cytopenias, increase in percentage of bone marrow blasts, or progression to a more advanced MDS FAB subcancer than pretreatment |
| Relapse After CR or PR | At least 1 of the following: Return to pretreatment bone marrow blast percentage Decrement of $\geq 50\%$ from maximum remission/response levels in granulocytes or platelets Reduction in Hgb concentration by ≥ 1.5 g/dL or transfusion dependence |
| Cytogenetic Response | Complete - Disappearance of the chromosomal abnormality without appearance of new ones Partial - At least 50% reduction of the chromosomal abnormality |
| Disease Progression | For subjects with: Less than 5% blasts: $\geq 50\%$ increase in blasts to $> 5\%$ blasts 5%-10% blasts: $\geq 50\%$ increase to $> 10\%$ blasts 10%-20% blasts: $\geq 50\%$ increase to $> 20\%$ blasts 20%-30% blasts: $\geq 50\%$ increase to $> 30\%$ blasts Any of the following: At least 50% decrement from maximum remission/response in granulocytes or platelets Reduction in Hgb by ≥ 2 g/dL Transfusion dependence |

KEY: CR = complete remission; DFS = disease-free survival; FAB = French-American-British; Hgb = hemoglobin; HI = hematologic improvement; IWG = International Working Group; MDS = myelodysplastic syndromes; PFS = progression free survival; PR = partial remission

^a Dysplastic changes should consider the normal range of dysplastic changes (modification).

^b Modification to IWG response criteria.

^d In some circumstances, protocol therapy may require the initiation of further treatment (e.g., consolidation, maintenance) before the 4-week period. Such subjects can be included in the response category into which they fit at the time the therapy is started. Transient cytopenias during repeated chemotherapy courses should not be considered as interrupting durability of response, as long as they recover to the improved counts of the previous course.

Notes: Subjects with CMML will be assessed for response using the IWG criteria for MDS. Deletions to IWG response criteria are not shown. To convert hemoglobin from grams per deciliter to grams per liter, multiply grams per deciliter by 10.

Source: Cheson BD, Greenberg PL, Bennett JM, Lowenberg B, Wijermans PW, Nimer SD et al. Clinical application and proposal for modification of the International Working Group (IWG) response criteria in myelodysplasia. Blood 2006; 108 (2): 419-25.

| Modified Hematologic Improvement According to IWG Criteria | |
|---|---|
| Hematologic improvement^a | Response criteria (responses must last at least 8 week)^b |
| Erythroid Response (HI-E) (pretreatment, <11 g/dL) | Hemoglobin increase by ≥ 1.5 g/dL Relevant reduction of units of RBC transfusions by an absolute number of at least 4 RBC transfusions/8 weeks compared with the pretreatment transfusion number in the previous 8 weeks. Only RBC transfusions given for a hemoglobin of ≤ 9.0 g/dL pretreatment will count in the RBC transfusion response evaluation ^b |
| Platelet Response (HI-P) (pretreatment, <100 X 10 ⁹ /L) | Absolute increase of ≥ 30 X 10 ⁹ /L for subjects starting with > 20 X 10 ⁹ /L platelets Increase from < 20 X 10 ⁹ /L to > 20 X 10 ⁹ /L and by at least 100% ^b |
| Neutrophil Response (HI-N) (pretreatment, <1.0 X 10 ⁹ /L) | At least 100% increase and an absolute increase > 0.5 X 10 ⁹ /L ^b |
| Progression or Relapse After HI ^c | At least 1 of the following: At least 50% decrement from maximum response levels in granulocytes or platelets Reduction in hemoglobin by ≥ 1.5 g/dL Transfusion dependence |

KEY: HI = hematologic improvement; HI-E = hematologic improvement erythroid response; HI-N = hematologic improvement neutrophil response; HI-P = hematologic improvement platelet response; IWG = International Working Group; MDS = myelodysplastic syndromes; RBC = red blood cell

^a Pretreatment counts averages of at least 2 measurements (not influenced by transfusions) ≥ 1 week apart (modification).

^b Modification to IWG response criteria.

^c In the absence of another explanation, such as acute infection, repeated courses of chemotherapy (modification), gastrointestinal bleeding, hemolysis, and so forth. It is recommended that the 2 kinds of erythroid and platelet responses be reported overall as well as by the individual response pattern.

Note: Deletions to the IWG response criteria are not shown. To convert hemoglobin levels from grams per deciliter to grams per liter, multiply grams per deciliter by 10.

Source: Cheson BD, Greenberg PL, Bennett JM, Lowenberg B, Wijermans PW, Nimer SD et al. Clinical application and proposal for modification of the International Working Group (IWG) response criteria in myelodysplasia. Blood 2006; 108 (2): 419-25.

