6.8.6. Transfusion Assessment

The following will be recorded for all transfusions the subject received within 56 days (8 weeks) prior to the first dose of IP, until 90 days after the last dose of CC-486 or durvalumab or the treatment discontinuation visit, whichever occurs later:

- type of transfusion (eg, pRBC or platelet)
- number of units
- reason for transfusion
- date of transfusion
- hemoglobin value for which any RBC transfusion is given
- platelet value for which any platelet transfusion is given

RBC transfusions administered for surgical procedures, significant hemorrhagic events, or other reasons documented as unrelated to MDS-associated anemia will not be counted in the assessment of baseline RBC transfusion requirements, efficacy, or progressive disease status.

RBC-transfusion-independent response or improvement will be assessed according to criteria modified from that of the International Working Group ([Appendix F](#)).

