 - worsening granulocytes should be $\geq 50\%$ decrease from pre-injectable HMA baseline value
 - worsening platelets should be $\geq 50\%$ decrease from pre-injectable HMA baseline value (untransfused)
 - worsening hemoglobin should be ≥ 1.5 g/dL decrease from pre-injectable HMA baseline value in subjects not receiving RBC transfusions
 - meaningful worsening in RBC or platelet transfusion requirement

Definition of *stable disease* is based on modified IWG 2006 criteria (Appendix F):

- Failure to achieve any objective response (CR, PR, mCR, or HI), but no evidence of disease progression within the 8 weeks leading to the subject's first dose of IP in this study (Cycle 1, Day 1).
5. Have the last dose of the prior treatment regimen (injectable HMA – azacitidine for injection or decitabine) not more than 16 weeks prior to screening for this study (date of informed consent signature).
 6. No less than 3 weeks between the last dose of the prior treatment regimen (injectable HMA – azacitidine for injection or decitabine) and the planned date of first dose of IP.

7. Have an ECOG performance status of 0, 1, or 2 ([Appendix E](#))
8. Females subjects of childbearing potential¹ may participate, providing they meet the following conditions:
 - a. Have two negative pregnancy tests as verified by the investigator prior to starting any IP therapy: serum pregnancy test at screening and negative serum or urine pregnancy test (investigator's discretion) within 72 hours prior to starting treatment with IP (Cycle 1, Day 1). They must agree to ongoing pregnancy testing during the course of the study (before beginning each subsequent cycle of treatment), and after the last dose of any IP. This applies even if the subject practices complete abstinence² from heterosexual contact.
 - b. Agree to practice true abstinence² (which must be reviewed on a monthly basis and source documented) or agree to the use of highly effective methods of contraception from 28 days prior to starting durvalumab or azacitidine, and must agree to continue using such precautions while taking durvalumab or azacitidine (including dose interruptions) and for up to 90 days after the last dose of durvalumab or azacitidine. Cessation of contraception after this point should be discussed with a responsible physician.
 - c. Agree to abstain from breastfeeding during study participation and for at least 90 days after the last dose of IP.

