9.1. Permitted Concomitant Medications and Procedures

Best supportive care may be used in combination with study therapy if deemed necessary. Best supportive care for this study includes, but is not limited to, treatment with RBC or whole blood transfusions, fresh frozen plasma transfusions, single donor or pooled donor platelet transfusions, antibiotic, antiviral and/or antifungal therapy, nutritional support as needed, and myeloid growth factors (G-CSF and GM-CSF) for subjects experiencing neutropenic infections. The use of myeloid growth factors is also allowed for secondary prophylaxis under certain conditions as described below. The use of these products will be considered as concomitant treatment and documented as concomitant medications, therapies or procedures.

Blood product support (RBCs and platelets) may be administered according to institutional standards. RBC and platelet transfusions will be considered concomitant procedures and should be collected on the appropriate CRF.

Subjects who are currently using iron-chelating agents should be on a stable or decreasing dose for at least 8 weeks (56 days) prior to enrollment. Initiation, modification, and/or discontinuation of iron-chelating agents during the treatment phase of the study is discouraged and should be discussed with the medical monitor first whenever possible.

Subjects may be administered supportive and palliative care (eg, pain control) as clinically indicated throughout the study.

It is recommended that an antiemetic medication such as a serotonin 5-HT₃ receptor antagonist (eg, ondansetron) be taken 30 minutes prior to IP administration during Cycle 1 of the treatment phase. If nausea/vomiting is not significant, further antiemetic prophylaxis may not be needed. Pre-treatment or post-treatment with a serotonin 5-HT₃ receptor antagonists, or other locally available and appropriate antiemetic medication, will be considered concomitant treatment and should be recorded on the appropriate CRF.

Treatment with antidiarrheal medications is recommended at the first sign of diarrhea as per the guidelines in [Appendix H](#). Pre-medication with antidiarrheal medication for subsequent doses of CC-486 and/or durvalumab may be appropriate. Pre- and post-treatment with an antidiarrheal must be recorded in the CRF as concomitant medication.

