Cytogenetic Response	Complete: – Disappearance of the chromosomal abnormality without appearance of new ones Partial: – At least 50% reduction of the chromosomal abnormality
Disease Progression	For subjects with: – Less than 5% blasts: $\geq 100\%$ increase in blasts to $\geq 8\%$ blasts – $\geq 5\%$ blasts: $\geq 50\%$ increase to $\geq 10\%$ blasts ^d Any clinical worsening from pre-injectable HMA baseline condition, including: – sustained clinically-significant worsening (investigator’s assessment) from baseline granulocyte, platelet, or hemoglobin values (≥ 2 values, separated by ≥ 2 weeks) o worsening granulocytes should be $\geq 50\%$ decrease from pre-injectable HMA baseline value o worsening platelets should be $\geq 50\%$ decrease from pre-injectable HMA baseline value o worsening hemoglobin should be ≥ 1.5 g/dL decrease from pre-injectable HMA baseline value – ongoing or worsening RBC or platelet transfusion requirement

Hematologic Response Modified from IWG Criteria for MDS (Cheson, 2006)	
Category	Response Criteria (responses must last at least 4 weeks)
Survival	Endpoints: 
 - Overall: death from any cause - Event free: failure or death from any cause - PFS: disease progression or death from any cause - DFS: time to relapse - Cause-specific death: death related to MDS

CR = complete remission; DFS = disease-free survival; FAB = French-American-British; Hgb = hemoglobin; HI = hematologic improvement; HMA = hypomethylating agent; IWG = International Working Group; mCR = marrow complete remission; MDS = myelodysplastic syndromes; PFS = progression-free survival; PR = partial remission; RBC = red blood cell; SD = stable disease; wks = weeks.

^a Dysplastic changes should consider the normal range of dysplastic changes (modification).

^b Modification to IWG (2000) response criteria.

^c In some circumstances, protocol therapy may require the initiation of further treatment (eg, consolidation, maintenance) before the 4-week period. Such subjects can be included in the response category into which they fit at the time the therapy is started. Transient cytopenias during repeated chemotherapy courses should not be considered as interrupting durability of response, as long as they recover to the improved counts of the previous course.

^d 20 – 30% blasts is considered AML according to the WHO classification (Vardiman, 2009).

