Notes: Deletions to the IWG response criteria are not shown. To convert hemoglobin from grams per deciliter to grams per liter, multiply grams per deciliter by 10.

Source: Cheson BD, Greenberg PL, Bennett JM, Lowenberg B, Wijermans PW, Nimer SD, et al. Clinical application and proposal for modification of the International Working Group (IWG) response criteria in myelodysplasia. *Blood*. 2006; 108(2): 419-25.

Hematologic Improvement According to IWG Criteria (Cheson, 2006)	
Hematologic improvement^a	Response criteria (responses must last at least 8 week)^b
Erythroid Response (HI-E) (pre-treatment, < 11 g/dL)	
 - Hemoglobin increase by ≥ 1.5 g/dL - Relevant reduction in units of RBC transfusions by an absolute number of at least 4 RBC transfusions/8 wk compared with the pretreatment transfusion number in the previous 8 wk
Platelet Response (HI-P) (pre-treatment, < 100 X 10 ⁹ /L)	
 - Absolute increase of $\geq 30 \times 10^9/L$ for subjects starting with $> 20 \times 10^9/L$ platelets - Increase from $< 20 \times 10^9/L$ to $> 20 \times 10^9/L$ and by at least 100%^b
Neutrophil Response (HI-N) (pre-treatment, < 1.0 X 10 ⁹ /L)	
 - At least 100% increase and an absolute increase $> 0.5 \times 10^9/L$^b
Progression or Relapse After HI ^c	At least 1 of the following: 
 - At least 50% decrease from maximum response levels in granulocytes or platelets - Reduction in Hgb by ≥ 1.5 g/dL - Transfusion dependence

KEY: HI-E = hematologic improvement-erythroid response; HI-N = hematologic improvement-neutrophil response; HI-P = hematologic improvement-platelet response; IWG = International Working Group; RBC = red blood cell.

^a Pre-treatment counts averages of at least 2 measurements (not influenced by transfusions, ie, no RBC transfusions for 2 weeks and no platelet transfusions for 1 week) ≥ 1 week apart (modification).

^b Modification to IWG (2000) response criteria.

^c In the absence of another explanation, such as acute infection, repeated courses of chemotherapy (modification), gastrointestinal bleeding, hemolysis, and so forth. It is recommended that the 2 kinds of erythroid and platelet responses be reported overall as well as by the individual response pattern.

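### SAP Appendix E differs from protocol Appendix F on transfusion response, progression and stable disease, so response and PFS results can depend on which table is programmed

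*SAP*

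**What the plan says.** Protocol 3.1 and 10.6.1 define objective response (CR, PR, marrow CR or HI) by protocol Appendix F. SAP 4.2.1 and 10.1 refer only to modified IWG 2006 criteria. SAP 15.5 (Appendix E) is the only response-criteria table in the SAP.

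On HI-E by transfusion, SAP Appendix E states: "Only RBC transfusions given for a hemoglobin of ≤ 9.0 g/dL pretreatment will count in the RBC transfusion response evaluation". Appendix F asks for the same reduction of at least 4 transfusions per 8 weeks but sets no haemoglobin limit. Protocol 9.1 says "Blood product support (RBCs and platelets) may be administered according to institutional standards". Protocol 6.8.6 excludes transfusions by reason, not by haemoglobin: those given for surgery, significant bleeding or "other reasons documented as unrelated to MDS-associated anemia will not be counted in the assessment of baseline RBC transfusion requirements, efficacy". For the HI baseline, Appendix F requires counts "not influenced by transfusions, ie, no RBC transfusions for 2 weeks and no platelet transfusions for 1 week"; the SAP footnote does not give these windows.

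On progression, SAP Appendix E measures blood counts from the best level reached: "At least 50% decrement from maximum remission/response in granulocytes or platelets". Appendix F measures from before the injectable agent: "Any clinical worsening from pre-injectable HMA baseline condition, including" falls in counts and "ongoing or worsening RBC or platelet transfusion requirement".

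On the assessor, protocol 10.6.1 has the investigator determine CR, PR and marrow CR, confirmed by a central reviewer, with HI derived. SAP 10.1 has the investigator determine all four, adds a separately analysed derived version, and does not mention central confirmation.

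**The concern.** A programmer who works from the SAP has one table to hand, and it is not the one the protocol names for the primary endpoint. HI counts towards that endpoint, so a different HI-E rule can change who is a responder. Progression ends PFS time and ends a response, so a different progression row can change both. SAP 10.1 also leaves open whether the investigator's or the derived response supplies the primary response rate. Two analysts could each follow an approved document and report different results.

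**Working it through.** **Figure in the plan.** The Simon design (stop at 2 or fewer of 16; reject at 8 or more of 41) reproduces. P(reject) = Σ over x = 3 to 16 of Bin(x; 16, p) × P[Bin(25, p) ≥ 8 − x], which gives 0.0995 at p = 0.125 and 0.801 at p = 0.27. The design is sound and the fix leaves it unchanged. The issue is what counts as a response.

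**The two tables side by side.** CR, PR, marrow CR, HI-P, HI-N, the haemoglobin route to HI-E, and relapse after HI agree. These contradict:

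| Item | Protocol Appendix F | SAP Appendix E |
|---|---|---|
| HI-E by transfusion | no haemoglobin limit | limit of 9.0 g/dL |
| Blasts, baseline <5% | rise ≥100% to ≥8% | rise ≥50% to >5% |
| Blasts, baseline ≥5% | rise ≥50% to ≥10% | rise ≥50%, to >10%, >20% or >30% by band |
| Haemoglobin fall | ≥1.5 g/dL | ≥2 g/dL |
| Reference for counts | pre-injectable-HMA baseline | maximum response (granulocytes, platelets) |
| Transfusion item | ongoing or worsening requirement | transfusion dependence |
| Stable disease | no CR, PR, marrow CR or HI | PR not reached |

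These are in the protocol but missing from the SAP: two values at least 2 weeks apart for CR/PR relapse and for cytopenic progression; the transfusion-free windows; the 6.8.6 exclusion; and central confirmation.

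**HI-E by transfusion, units per 8 weeks.** A response needs a fall of at least 4.
- Before treatment 6 units, 3 of them given above 9.0 g/dL; on study 2 units. Protocol: 6 − 2 = 4, response. SAP: the counted baseline is 3, so a fall of 4 is impossible.
- Before treatment 6 units, all at or below 9.0; on study 6 units, 4 of them above 9.0. Protocol: 6 − 6 = 0, no response. SAP: 6 − 2 = 4, response, if the limit also applies on study; 6 − 6 = 0 if it applies only before treatment. The clause does not settle which.

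So the limit can act in either direction. Each example assumes the change lasts the required 8 weeks and that the subject does not respond by the haemoglobin route.

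**Blasts.** 4% to 6%: the rise is 50%, to above 5% but below 8%, so progression in the SAP only. 12% to 18%: the rise is 50%, to at least 10% but not above 20%, so progression in the protocol only. Over integer baselines 1–29% and follow-up values 1–45% (29 × 45 = 1,305 pairs), 10 pairs are protocol-only and 8 SAP-only. If baselines of 10% and 20% go to the upper SAP band, the counts are 17 and 8. These counts show that the rules differ both ways, not how many patients are affected.

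**Size for the response rate.** One subject moves the rate by 100/n points. At the planned n = 16 this is 100/16 = 6.25. The final cohort sizes are not stated. 65 enrolled less 13 in the monotherapy run-in leaves 52; assuming c in the combination run-in, the two Phase 2 cohorts average (52 − c)/2. That is 24.5 at c = 3, 20 at c = 12 and 16 at c = 20. The shift is 5.0 points at n = 20 and 4.2 at n = 24. As illustrations at n = 16, exact 95% intervals are 0.2–30.2% for one responder and 1.6–38.3% for two. At the 90% level SAP 10.1 uses for cohort rates, they are 0.3–26.4% and 2.3–34.4%.

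**Why the progression row cannot simply be copied.** PFS starts at first dose, but the Appendix F row looks back to before the injectable agent and includes an ongoing transfusion need. The entry definition of progression in protocol 7.2 is narrower ("meaningful worsening in RBC or platelet transfusion requirement"). Read literally, some subjects could meet the Appendix F row on day 1.

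**The case against.** **The protocol already governs.** It names Appendix F, and the SAP body never calls on Appendix E. Silence in the SAP does not cancel the 6.8.6 exclusion, the repeat-value rule or central confirmation. This stands in part: those items are omissions, not reversals. But the HI-E, progression and stable-disease rows positively conflict. The SAP's own amendment table records only PK outputs and the AESI list, so nothing marks the differences as intended.

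**Stable disease.** A reader might infer that the stable-disease endpoint has two definitions. It does not: protocol 10.6.2.5 and SAP 10.2.5 give the same rule. The Appendix E wording reaches the best-response table, where a subject with HI or marrow CR alone could also be classed as stable.

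**Confirmation.** A reader might infer that the SAP accepts any single progression value. SAP 10.2.5 requires two observations at least 8 weeks apart, although it sits under stable disease and SAP 10.2.4 does not say it applies to PFS.

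**Stage 1.** A reader might infer that the decision to close the cohorts turned on the wrong table, or that it was safely made on Appendix F. Neither is shown. Protocol 4.1.3 plans the use of Appendix F, SAP section 2 plans a first-stage analysis under the SAP, and the Amendment 4 justification says only that too few responses were seen. Nor does that cap each cohort at two responders: best response has no cycle limit, and five Phase 2 subjects were still on treatment.

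**Impact.** Enrolment is closed and no Stage 2 test remains, so the effect is on descriptive estimates. That stands.

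**The ongoing-requirement item.** It sits under a heading about worsening and can be read narrowly. That is fair, and is why a check is enough.

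**Conclusion.** The concern holds and should be fixed before reporting. The three contradictions (HI-E transfusion counting, progression, and the stable-disease row) and the listed omissions are in the current text of both documents. Overall response rate, best response, PFS and duration of response can each differ according to the document followed.

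Confidence is high on the textual differences and limited on their consequences. The documents do not give the number of subjects affected, the final responder counts, or the table used at Stage 1. The shift of 6.25 points per reclassified responder assumes 16 subjects in the cohort; the smaller shifts rest on the assumed size of the combination run-in.

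**What to change.** 1. Amend SAP Appendix E so that its response, HI, stable-disease and CR/PR relapse criteria reproduce protocol Appendix F, with the 2-week and 1-week transfusion-free windows and the 6.8.6 exclusion. Remove the 9.0 g/dL clause and the stable-disease wording that refers only to PR.
2. State in SAP 10.1 that the primary response rate follows protocol 10.6.1: CR, PR and marrow CR by the investigator with central confirmation, and HI derived.
3. Reconcile Appendix F, protocol 10.6.2.5 with SAP 10.2.5, and SAP Appendix E into one on-study progression definition for the PFS and duration-of-response analyses. It should state the blast rule, reference point, transfusion wording and confirmation. The choice of reference is the sponsor's. Check that no subject already meets the definition at first dose. Protocol Table 8 serves discontinuation decisions and stays as it is.

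The cost is a SAP amendment and re-derivation of response and progression, mostly from collected data. Two inputs may be incomplete: values from before the injectable agent, since protocol 6.1.1 asks for past reports only where possible, and haemoglobin before historical transfusions, which protocol 4.1.1 requires only if available. The second gap is a further reason to drop the 9.0 g/dL clause, because the SAP has no rule for a missing value.
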